To date there is very little PD and pharmacokinetic (PK) data on the ticagrelor 60 mg bid dosing regimen. In particular, there is no prospective PK/PD study on this dosing regimen in patients with DM who are known to have impaired response to clopidogrel therapy. Since DM patients frequently require elective PCI due to chronic progression of CAD (and not solely because of an acute thrombotic complication), and clopidogrel remains the guideline recommended P2Y₁₂ inhibiting therapy for these patients, understanding the PD effects of the ticagrelor 60 mg bid regimen in this setting is an unmet clinical need. This is also in light of the ongoing THEMIS trial which is specifically evaluating the impact of the ticagrelor 60 mg bid dosing regimen in type 2 DM patients without a prior major CV event.

[figure not shown]
REASERCH PLAN

Study design

The proposed investigation will be a prospective, randomized, open-label, PK/PD study conducted in DM patients undergoing elective PCI. Figure 1 illustrates the overall study design. After providing written informed consent and following diagnostic angiography, patients meeting study entry criteria (see inclusion and exclusion criteria below) undergoing PCI will be randomly assigned in a 1:1 ratio to treatment with either ticagrelor or clopidogrel. Patients randomized to ticagrelor will receive ticagrelor 180 mg loading dose (LD) followed by a 60 mg bid MD starting 12 h (\pm 1 h) after the LD. Patients randomized to clopidogrel will receive a 600 mg LD followed by a 75 mg od MD starting 24 hours (\pm 1 h) after the LD. Maintenance dose therapy will be maintained for 30 \pm 3 days. All patients will receive a 325 mg LD of aspirin prior to the procedure and then 81 mg daily. Afterwards, antiplatelet treatment will be left to the discretion of the treating physician.

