The randomized treatment will be administered in the catheterization laboratory after defining coronary anatomy and before starting PCI (defined as before guide wire passing the target coronary lesion). Blood samples for PK/PD testing will be obtained at a total of 9 time points: immediately before the LD, and then at 0.5 h, 2 h, 8 h, 24 h (trough and peak), and 30 (\pm 3) days (trough and peak) following LD; an additional sample will be collected at the end of PCI. The end of PCI is defined as when the guide catheter is removed from the body at the completion of the procedure. Access site, choice of anticoagulant (i.e., heparin or bivalirudin), stent type and procedural technique will be at the discretion of the physician. Staff performing PK/PD assessments will remain blinded to treatment assignment.

The study will be performed at the University of Florida Health Science Center at UF Health Jacksonville - Division of Cardiology. Patients will be recruited prior to undergo diagnostic angiography at the inpatient and outpatient facilities of our institution and will be screened by Cardiology Research staff, who will verify that all candidates meet inclusion and exclusion criteria. Results from blood tests performed within the last 30 days will be considered valid for screening purposes. If these are not available, a blood sample will be collected for the screening phase.

Study Population

Specific inclusion and exclusion criteria are described below and have been considered to closely reflect study entry criteria of the THEMIS trial (NCT01991795).

Inclusion criteria

For inclusion in the study patients should fulfill the following criteria:

1. Provision of informed consent prior to any study specific procedures
2. Men or women ≥ 18 years of age
3. Diagnosed with type 2 DM defined by ongoing glucose lowering drug (oral medications and / or insulin) treatment for at least 1 month
4. Presence of CAD undergoing elective PCI*

* Patients will need to be cardiac enzyme-negative prior to undergoing coronary angiography.

Patient will need to be on a background of aspirin therapy (treated with a 325 mg LD prior to coronary angiography unless already on chronic low-dose aspirin therapy). Patients on maintenance clopidogrel 75 mg therapy for at least 1 week due to a prior vascular intervention will also be eligible. However, patients on clopidogrel, ticagrelor or prasugrel due to a prior acute major cardiovascular event (MI or stroke) will not be eligible.

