17. Women of child-bearing potential (ie, those who are not chemically or surgically sterilized or who are not post-menopause) who are not willing to use a medically accepted method of contraception that is considered reliable in the judgment of the investigator OR who have a positive pregnancy test at enrolment or randomization OR women who are breast-feeding. If a subject becomes pregnant during the course of the study the investigational product should be discontinued immediately [the outcome of all pregnancies (spontaneous miscarriage, elective termination, ectopic pregnancy, normal birth or congenital abnormality) will be followed up and documented even if the subject was discontinued from the study].
18. Inability of the patient to understand and/or comply with study procedures and/or follow up, in the opinion of the investigator, OR any conditions that, in the opinion of the investigator, may render the patient unable to complete the study
19. Life expectancy of less than 1 month based on investigator's judgement
20. Participation in another clinical study with an investigational (defined as non-FDA approved) product within 28 days prior to enrolment
21. Previous randomization in the present study

Blood sampling and PK/PD Assessments

Blood samples for screening procedures if needed will be obtained via antecubital vein puncture using a 21-gauge needle. Blood samples for PK/PD testing at baseline (before the LD), at 0.5 h, and at the end of the PCI will be collected from the arterial access site sheet; blood samples for the 2 h, 8 h, 24 h (trough and peak), and 30±3 days (trough and peak) time points will be collected via antecubital vein puncture using a 21-gauge needle. The last dose intake of study drug will be 12±2 h and 24±2 h prior to blood sampling in order to guarantee assessment of trough level of platelet inhibition for ticagrelor and clopidogrel, respectively, while peak levels of platelet inhibition will be assessed by obtaining blood samples 2 h after MD administration (22). The first few mL of blood will be discharged in order to avoid spontaneous platelet activation. Whole blood samples will be collected into 3.2% 9NC Coagulation Sodium Citrate, 2mL (Vacurette, Kremsmünster, Austria) and 3.2% Buffered Sodium Citrate, 4.5mL (BD, Franklin Lakes, NJ, USA) tubes as appropriate for the specific assays being conducted.

PD assessments

A total of 3 different PD assays will be used for this study:

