3) *Light transmittance aggregometry (LTA):* Platelet aggregation will be performed using LTA according to standard protocols. LTA will be assessed using platelet-rich plasma (PRP) by the turbidimetric method in a 2-channel aggregometer (Chrono-Log 490 Model, Chrono-Log Corp., Havertown) as previously described (3). Platelet agonists will include arachidonic acid (AA; 1 mM), collagen (3µg/ml) and ADP (5 and 20 µM) and TRAP (15 µM). PRP will be obtained as a

supernatant after centrifugation of citrated blood at 1000 rpm for 10 minutes. The isolated PRP will be kept at 37° C before use. Platelet-poor plasma (PPP) will be obtained by a second centrifugation of the blood fraction at 2800 rpm for 10 minutes. Light transmission will be adjusted to 0% with the PRP and to 100% for the PPP for each measurement. Curves will be recorded for 6 minutes and platelet aggregation will be determined as the maximal percent change (MPA) and late platelet aggregation (LPA) in light transmittance from baseline using PPP as a reference.

PK assessments

PK assessments will include determination of plasma concentration of clopidogrel active metabolite, ticagrelor and its active metabolite (AR-C124910XX), as previously described (3,26). Time for the maximum plasma concentration (T_{max}), maximum observed plasma concentration (C_{max}) and the area under the plasma concentration vs. time curve from time 0 to the last measurable concentration (AUC_{0-t}) will be calculated.

Other laboratory assessments

Blood samples will also be collected to assess the following parameters: a) HbA1c at baseline; b) reticulated platelets at baseline and 30 days; c) troponin levels at baseline, and 6 h and 24 h post PCI.

Study endpoints, sample size calculation and statistical analysis

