Secondary endpoints will include comparisons of measures of platelet reactivity using VN, VASP, and LTA at all other time points [0.5 h, 8 h, 24 h (trough and peak), 30 days (trough and peak) following LD, and end of PCI] as well as rates of high on-treatment platelet reactivity (HPR). In line with recent expert consensus definitions, HPR will be defined as a PRU >208, VASP-PRI > 50%, maximum LTA response to 20 μ M ADP > 59 %, maximum LTA response to 5 μ M ADP > 46 % (28). In addition, time for the maximum plasma concentration (T_{max}), maximum observed plasma concentration (C_{max}) and the area under the plasma concentration vs. time curve from time 0 to the last measurable concentration (AUC_{0-t}) of plasma concentration of clopidogrel active metabolite, ticagrelor and its active metabolite (AR-C124910XX) will be calculated.

All patients who received at least 1 dose of study drug will be included in the safety population. Safety will be evaluated by assessment of adverse events (including bleeding and ischemic), serious adverse events, physical examination, and vital signs. Adverse events will be collected up to 7 days after the completion of the study. Bleeding events will be classified according to BARC (Bleeding Academic Research Consortium) criteria (29). Stent thrombosis

will be classified according to ARC (Academic Research Consortium) definitions (30). MI, including peri-procedural MI, will be defined according to the universal definition (31). Ischemic stroke will be defined as an ischemic cerebral infarction caused by an embolic or thrombotic occlusion of a major intracranial artery. Death will be considered cardiac in origin unless obvious non-cardiac causes can be identified.

Possible Discomforts and Risk

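### Does AUC0-t need a stated end point, given that sampling runs past later doses and a ticagrelor value to the 24 h trough would mix loading and maintenance doses?

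*Combined protocol and SAP*

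**What the plan says.** The section on PK assessments lists Tmax, Cmax and AUC0-t, the last being the "area under the plasma concentration vs. time curve from time 0 to the last measurable concentration". The secondary-endpoint paragraph repeats this and says that the parameters "of plasma concentration of clopidogrel active metabolite, ticagrelor and its active metabolite (AR-C124910XX) will be calculated". Neither place gives a visit, clock time or dosing interval for t, or separates day 1 from day 30.

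The dose times are in the Study design section. Ticagrelor is a 180 mg loading dose "followed by a 60 mg bid MD starting 12 h" later (±1 h). Clopidogrel is a "600 mg LD followed by a 75 mg od MD starting 24 hours" later (±1 h).

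The same section sets the blood draws: "immediately before the LD, and then at 0.5 h, 2 h, 8 h, 24 h (trough and peak"), then trough and peak at 30 days; "an additional sample will be collected at the end of PCI". The section on blood sampling fixes what trough and peak mean. "The last dose intake of study drug will be 12±2 h and 24±2 h prior to blood sampling" for ticagrelor and clopidogrel respectively, and peak means "obtaining blood samples 2 h after MD administration".

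**The concern.** An AUC that ends at the last measurable concentration has a clear meaning when one dose is followed until it clears. Here patients are dosed repeatedly while sampling goes on, so the content of the AUC depends on a choice of t that the plan leaves open. Under one natural choice, the 24 h trough, the same symbol stands for two doses in one arm and one study dose in the other.

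What would be at stake is interpretation. The Study rationale cites scarce PK data on the 60 mg twice-daily regimen. A reader could take a ticagrelor AUC0-t as exposure on that regimen when most of it comes from the 180 mg load. Day 30 offers only a trough and a 2 h post-dose sample, so no observed AUC over a 60 mg interval can be formed. An open t could also be chosen after the concentrations are seen, or differ between patients and analytes.

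**Working it through.** The documents state no AUC figure, so there is none to reproduce. The first two steps use only the documents. The remaining steps are an illustration of size.

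**1. When the 24 h trough falls.**
- Ticagrelor: first maintenance dose at 11-13 h, trough 10-14 h after it, so 11 + 10 = 21 h to 13 + 14 = 27 h after the load. This is always after the 12 h dose.
- Clopidogrel: 22-26 h after the load, with no study dose in between. (Some patients may enter on maintenance clopidogrel, hence *study* dose.)
- Draws scheduled between 8 h and the 24 h trough: none.

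**2. Study doses inside each possible window.**

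| AUC ends at | Ticagrelor | Clopidogrel |
|---|---|---|
| 8 h | load | load |
| 24 h trough | load + 1 maintenance | load |
| 24 h peak | load + 2 maintenance | load + 1 maintenance |

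The structural part of the concern is therefore correct, if t is the 24 h trough.

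**3. Size for ticagrelor.** Assumptions, not from the documents: one compartment, half-life 4-12 h (ke = ln 2 / half-life), absorption ka 0.8-2.5 per h, end of PCI at 0.75-1.5 h, linear trapezoid. In arbitrary units, a dose D given at time s contributes

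C(t) = D · ka/(ka − ke) · [exp(−ke(t − s)) − exp(−ka(t − s))].

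Worked case: half-life 8 h (ke = 0.0866), ka = 1.6, end of PCI at 1 h, 180 mg at 0 h and 60 mg at 12 h.
- Concentrations at 0, 0.5, 1, 2, 8 and 24 h: 0, 96.7, 136.1, 152.3, 95.2, 46.2.
- Trapezoid: 24.2 + 58.2 + 144.2 + 742.3 + 1130.9 = 2099.8.
- True exposure over 24 h: 1802.9 (load) + 433.6 (12 h dose) = 2236.6 after rounding.
- Share from the 12 h dose: 433.6 / 2236.6 = 19.4%.
- Trapezoid against load alone: 2099.8 / 1802.9 = 1.165.
- Trapezoid against combined exposure: 2099.8 / 2236.6 = 0.939.
- Share of the trapezoid from the single 8-24 h segment: 1130.9 / 2099.8 = 54%.

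Over the full grid:

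| Quantity | Range |
|---|---|
| 12 h dose as share of true 0-24 h exposure | 17-23% |
| Trapezoid to 24 h, above loading-dose AUC0-24 | 12-24% |
| Same, dose ±1 h and trough ±2 h both varied | 10-29% |
| Trapezoid to 24 h, below true combined exposure | 4-8% |
| Same, both windows varied | 1-9% |
| Trapezoid to 26 h (24 h peak), above loading-dose AUC0-26 | 16-30% |

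**4. Cmax and Tmax.** In the worked case the 26 h concentration is 89.6, and 89.6 / 152.3 = 59% of the highest loading-dose sample. Over the grid, the 26 h sample is 39-87% and the day-30 2 h sample 38-76% of the highest of the 0.5, 2 and 8 h values. Later samples never become the maximum, so neither parameter changes.

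**5. What closing at 8 h would buy.** The 0-8 h window isolates the load in both arms, but it captures only 44-74% of loading-dose AUC0-24, and its trapezoid is off by −8% to +4%. That is no clear gain in accuracy over a combined 0-24 h value.

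**The case for a change.** The best argument for a change is that it costs one sentence. A descriptive number still needs a defined meaning, and the document calls itself a PK/PD study. Read literally, the last measurable concentration could even be the day-30 peak, with one straight segment spanning about four weeks of dosing. The sources cited for the PK work are cited for determining concentrations, and nothing in the protocol says that they fix t for this schedule.

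Much of this stands: t is unspecified, and nothing elsewhere in the document supplies it. What does not stand is the step from an open t to an error. The plan never ends the AUC at the 24 h trough, and never calls it loading-dose exposure or exposure on 60 mg twice daily, so a value to 24 h would fit the stated definition. The plan does not promise a steady-state AUC either, and the day-30 trough and peak samples already provide concentrations on the maintenance regimen. The difference between arms feeds no stated comparison: the analytes are different molecules, and the analysis-of-variance text on other intergroup comparisons does not name PK. Joining the 24 h and day-30 samples into one curve is a reading that a competent PK analyst would reject.

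**Conclusion.** The gap is real and minor. It is missing detail in a descriptive secondary PK measure, of a kind that analysts fill sensibly by stating the window beside the value and describing a ticagrelor 0-24 h figure as load plus first maintenance dose. If that label were left off and a reader took the figure as loading-dose exposure alone, the overstatement would be about 12-24%, or 10-29% with the timing windows. As combined exposure it is within about 4-8%. The obvious replacement, an 8 h window, is a trade-off rather than an improvement. The primary endpoint, the platelet-reactivity comparisons and, in the illustration, ticagrelor Cmax and Tmax are unaffected.

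The dose counts rest on the documents alone. The percentages rest on assumed half-lives and absorption rates for ticagrelor. AR-C124910XX and clopidogrel active metabolite were not modelled, so no size is claimed for them. No change to the plan is needed.

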The primary endpoint of our study will be platelet reactivity, measured as PRU level using VN, of ticagrelor versus clopidogrel MD at 30 days after PCI, immediately pre-dosing dosing (trough levels). Based on previous studies (22,24,27), assuming a standard deviation of 55 and 100 PRU for ticagrelor and clopidogrel, respectively, a sample size of 34 patients (17 per treatment group) will be needed to detect an absolute difference of 95 PRU between ticagrelor and clopidogrel (corresponding to means of 170 versus 75) with a 90% power and a 2-tailed alpha value of 0.05. Assuming a potential 25% in data attrition due to patient drop-out (e.g., due to side effects, unplanned use of parenteral antiplatelet therapies after randomization or withdrawal of consent) or invalid PD samples (e.g, due to hemolysis or technical reasons), a sample size of approximately 42 patients is expected to be randomized.

Conformity to the normal distribution will be evaluated for continuous variables with the Shapiro-Wilk test. For baseline characteristics, continuous variables will be expressed as mean (standard deviation [SD]) and categorical variables as frequencies and percentages. Chi-squared test or Fisher's exact test will be used where appropriate to compare categorical variables between 2 groups.

The PD population will include all patients with PD data and without a major protocol deviation thought to affect significantly the PD of ticagrelor or clopidogrel. The PD population will be used for analysis of all primary and secondary PD variables. Erroneously treated patients (eg, those randomized to one treatment but actually given the other) will be accounted for based on the actual treatment received.

The primary analysis of the difference between ticagrelor and clopidogrel in PRU will be analyzed using analysis of variance. Treatment level means and 2-sided 95% confidence intervals (CIs) will be estimated. Analysis of variance will also be used to evaluate other intergroup comparisons. Repeated measures of analysis of variance, taking into account between- and within-subject variations, will be conducted to evaluate the impact of the 2 different treatments on platelet reactivity across time points. A p-value < 0.05 will be considered statistically significant. Statistical analysis will be performed with SPSS version 24 software (SPSS Inc.).

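### The primary analysis of 30-day trough PRU leaves out the pre-loading-dose PRU that the trial already plans to collect; prespecifying it as a covariate is a low-cost optional improvement

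*Combined protocol and SAP*

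**What the plan says.** In its section on study endpoints, sample size and statistical analysis, the combined protocol and SAP states: "The primary analysis of the difference between ticagrelor and clopidogrel in PRU will be analyzed using analysis of variance". Treatment means with two-sided 95% confidence intervals follow. The same approach extends to the remaining comparisons: "Analysis of variance will also be used to evaluate other intergroup comparisons". No covariate is named there or anywhere else. A repeated-measures ANOVA across time points is also planned, but as a separate analysis; nothing says that it adjusts the primary estimate.

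Other sections bear on this:

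- Study design, on allocation: patients are "randomly assigned in a 1:1 ratio to treatment with either ticagrelor or clopidogrel". No stratification factor is given.
- Study design, on sampling: "Blood samples for PK/PD testing will be obtained at a total of 9 time points: immediately before the LD". The sample is not restricted to a subset.
- Inclusion criteria: "Patients on maintenance clopidogrel 75 mg therapy for at least 1 week due to a prior vascular intervention will also be eligible". Patients not taking a P2Y12 inhibitor can also enter.
- Blood sampling, on the first draws: "Blood samples for PK/PD testing at baseline (before the LD), at 0.5 h, and at the end of the PCI will be collected". These are arterial, whereas the later samples, including day 30, are venous: "time points will be collected via antecubital vein puncture using a 21-gauge needle".

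**The concern.** A baseline measurement of the primary outcome is usually the first candidate for a covariate in a small randomised trial. Here it is already scheduled, on the same assay. It is also likely to vary widely, because patients on clopidogrel and patients on no P2Y12 inhibitor may both enter. With some 31 to 34 evaluable patients and no stated stratification, the arms can differ in baseline PRU by chance.

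If pre-LD PRU predicts day-30 PRU, adjustment narrows the confidence interval without another blood draw. If it does not, adjustment costs one degree of freedom and a little precision. The decision has to be made before data are seen, since a covariate added later would look selective. What is at stake is modest precision, not the validity of the comparison.

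**Working it through.** **Inputs from the statistical section.** SD 55 (ticagrelor) and 100 (clopidogrel); difference 170 − 75 = 95 PRU; two-sided alpha 0.05; target power 90%; 34 evaluable (17 per arm); about 42 randomised; 25% attrition.

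**Assumed.** rho, the correlation between pre-LD and day-30 PRU, is varied from 0 to 0.5.

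**Step 1: reproduce the plan's figure.** Mean variance = (55² + 100²)/2 = 6512.5, so the SD is 80.7. At n = 34, SE = √(6512.5 × 4/34) = 27.7, noncentrality = 95/27.7 = 3.43, df = 32. Noncentral-t power is 91.4%. With 16 per arm it is 89.6%, so 17 per arm is the smallest size that reaches 90%. The stated sample size is right for the unadjusted analysis.

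**Step 2: apply the plan's own attrition.** 42 × 0.75 = 31.5, taken as 31. SE = √(6512.5 × 4/31) = 29.0, df = 29, power 88.6%, CI half-width 59.3 PRU.

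**Step 3: add one covariate.** Variance of the difference = 6512.5 × (1 − rho²) × (4/n) × (1 + 1/(n − 4)), with df = n − 3. The last factor is the average cost of chance baseline imbalance. For n = 31 and rho 0.3, SE = √(6512.5 × 0.91 × 4/31 × 28/27) = 28.2.

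| | Unadjusted | rho 0 | 0.2 | 0.3 | 0.4 | 0.5 |
|---|---|---|---|---|---|---|
| Power, n = 31 | 88.6% | 87.4% | 88.7% | 90.2% | 92.3% | 94.8% |
| Half-width, n = 31 (PRU) | 59.3 | 60.5 | 59.2 | 57.7 | 55.4 | 52.4 |
| Power, n = 34 | 91.4% | 90.5% | 91.6% | 92.9% | 94.6% | 96.5% |
| Half-width, n = 34 (PRU) | 56.4 | 57.4 | 56.2 | 54.7 | 52.6 | 49.7 |

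The half-widths break even at rho 0.20 (n = 31) and 0.19 (n = 34). Reaching 90% power at n = 31 needs rho of about 0.29.

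**Step 4: let rho differ by arm.** The ticagrelor arm is expected to vary less, so its correlation may be lower. Simulation at n = 31 with SDs 55 and 100 (40,000 trials per cell):

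| rho ticagrelor, clopidogrel | ANCOVA power | ANOVA power | CI width ratio |
|---|---|---|---|
| 0, 0.3 | 88.5% | 88.5% | 1.001 |
| 0.1, 0.3 | 88.7% | 88.4% | 0.994 |
| 0, 0.5 | 90.3% | 88.4% | 0.968 |
| 0.1, 0.5 | 91.0% | 88.4% | 0.957 |

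**Step 5: mix the baseline.** Assume 35% of patients are on clopidogrel at entry, with pre-LD PRU 80 lower, a baseline SD of 60 and no carry-over to day 30. Within-group correlations of 0.3 and 0.5 become 0.25 and 0.42 overall. ANCOVA power at n = 31 is 89.1% and 92.3%, with CI width ratios of 0.989 and 0.932.

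**Step 6: type I error.** Over rho 0, 0.3, 0.5 and the unequal pair (0.1, 0.5), with ticagrelor listed first:

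- Split 16/15: 5.3–5.6% for ANCOVA, 5.3–5.9% for ANOVA.
- Split 15/16: 4.8–5.0% and 4.7–5.1%.
- Split 17/17: 5.0–5.3% and 5.0–5.4%.

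**Step 7: missing baselines.** With 10% of pre-LD values missing and replaced by the mean over both arms, power at n = 31 is 87.4%, 89.5%, 91.3% and 93.5% at rho 0, 0.3, 0.4 and 0.5. Type I error is 5.7%, against 5.7–5.8% for ANOVA.

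**Step 8: early time points.** Take the mixture of step 5, SD 80.7 in both arms, 16 per arm, and an assumed carry-over of the prior clopidogrel effect. CI width ratios:

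| Carry-over (PRU) | rho 0 | 0.3 | 0.5 |
|---|---|---|---|
| 0 | 1.018 | 0.985 | 0.924 |
| 40 | 1.011 | 0.947 | 0.862 |
| 80 | 0.992 | 0.905 | 0.807 |

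Two of the nine cells are wider and seven narrower. All inputs to this step except the SD of 80.7 are assumptions outside the documents.

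**The case against.** The strongest reply is that nothing is broken. The ANOVA is sound under randomisation, its sample size reproduces, and every gain depends on a correlation that the documents do not supply. The plan itself gives reasons to expect a low one: arterial blood at baseline against venous blood at day 30, a smaller spread on ticagrelor, and a baseline that is on-drug for some patients and untreated for others. The scenarios that reflect these features show the least benefit. With rho 0 on ticagrelor and 0.2 on clopidogrel, a 16/15 split gives 87.9% for ANCOVA against 88.6%, a small net loss. The shortfall at 31 evaluable comes from how attrition was allowed for, not from the missing covariate. The early-time-point figures rest almost wholly on assumed inputs.

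All of that stands, and it is why this is optional. It does not remove the case for the change, because the loss is bounded at about 1 point of power while the possible gain is several times larger.

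A further objection concerns the model-based SE, which was examined above only for nearly equal arms. At an assumed split of 18 ticagrelor to 13 clopidogrel, type I error rises to about 6.7–7.6% for ANCOVA. It is 7.3–7.7% for the planned ANOVA, so this limits both models and does not favour leaving the covariate out.

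**Conclusion.** The point holds as an optional improvement. The plan names no covariate for the primary comparison, a suitable one is scheduled in every patient, and a separate repeated-measures analysis does not fill the gap. The unadjusted ANOVA remains acceptable, with computed power of 91.4% at 34 evaluable against the 90% stated.

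If rho is the same in both arms, adjustment at 31 evaluable changes power by −1.2 to +6.2 points over rho 0 to 0.5 (87.4% to 94.8%, against 88.6%). The interval goes from 2% wider to about 12% narrower (60.5/59.3 and 52.4/59.3). If the correlation is weaker on ticagrelor, the day-30 gain is small or nil. Gains are more plausible soon after the LD, when earlier clopidogrel may still act; the half-hour and end-of-PCI samples also share the arterial site with baseline.

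Confidence is medium, because rho is unknown. The conclusion assumes the plan's SDs and difference, one linear covariate and nearly equal arms.

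**What to change.** Before any data are seen, amend the statistical section as follows.

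1. Make the primary analysis an ANCOVA of 30-day trough PRU on treatment and pre-LD PRU, with the usual model-based SE. Report the adjusted difference with its 95% CI.
2. Keep the unadjusted ANOVA as a supportive analysis.
3. Replace a missing or invalid pre-LD value with the mean pre-LD PRU over both arms, so that no patient with a day-30 value is lost.
4. Use each assay's own pre-LD value in the same way for the VerifyNow, VASP and aggregometry comparisons at other time points. State that all three assays are run on the pre-LD sample; the time points listed with the secondary endpoints do not include it.
5. State whether the pre-LD value enters the repeated-measures ANOVA as a covariate or as a time point.

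The cost is SAP wording. No sample or visit is added, and the model is the planned one plus one covariate, so the named software need not change. If baseline proves uninformative, the price is one degree of freedom, about 1 point of power and a 2% wider interval: 90.5% rather than 91.4% at 34 evaluable, and 87.4% rather than 88.6% at 31.

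### The across-time repeated-measures ANOVA, if run in the usual SPSS procedure, would drop every patient missing one sample; a mixed model would keep the valid ones

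*Combined protocol and SAP*

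**What the plan says.** All analysis text is in the combined protocol and SAP, section *Study endpoints, sample size calculation and statistical analysis*.

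- **Method.** For the effect of the two treatments over time, "Repeated measures of analysis of variance, taking into account between- and within-subject variations, will be conducted". The software is SPSS version 24. No SPSS procedure, covariance structure, list of time levels or rule for a missing sample is given. For the rest, "Analysis of variance will also be used to evaluate other intergroup comparisons".
- **Expected losses.** The sample-size paragraph reads "Assuming a potential 25% in data attrition due to patient drop-out" and adds "invalid PD samples (e.g, due to hemolysis or technical reasons" as a further cause. About 42 patients are to be randomized so that 34 are evaluable.
- **Population.** "The PD population will include all patients with PD data and without a major protocol deviation" thought to affect the drugs' pharmacodynamics significantly. This rule works at patient level and does not cover a patient with some samples missing.
- **Time points.** *Study design* says "Blood samples for PK/PD testing will be obtained at a total of 9 time points: immediately before the LD". The secondary-endpoint paragraph compares the assays "at all other time points [0.5 h, 8 h, 24 h (trough and peak), 30 days (trough and peak) following LD", plus end of PCI. That is seven times, without the pre-LD and 2 h samples.

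**The concern.** In SPSS, repeated-measures ANOVA ordinarily means GLM Repeated Measures, with one column per time level. It analyzes only patients who have every level. That is general knowledge of the software; the documents do not say it. With up to nine levels over 30 days and losses expected by the plan itself, one absent or hemolyzed sample would remove all of a patient's data from the analysis.

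Two things are at stake. The only named analysis of the whole time course would be less precise than the collected data allow. It could also rest on a different set of patients from the single-time-point comparisons reported beside it, so that the two could disagree simply because of who was dropped. If the procedure and levels are left open, they are chosen after the data are seen.

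**Working it through.** **The plan's own figure.** The stated 17 per group for the primary comparison reproduces. With average SD √((55² + 100²)/2) = 80.7, difference 95 and two-sided alpha 0.05, noncentral-t power is 0.896 at 16 and 0.914 at 17 per group. The plan gives no sample size or power for the across-time analysis.

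**Samples at risk.** The nine samples are pre-LD, 0.5 h, end of PCI, 2 h, 8 h, 24 h trough, 24 h peak, day-30 trough and day-30 peak. Seven precede day 30. That falls to six if pre-LD is not a level, and to five under the secondary-endpoint list. If 8 to 11 of 42 patients were lost before day 30, complete-case analysis would discard 8 × 7 = 56 to 11 × 7 = 77 valid samples out of 42 × 7 = 294 (40 to 55 under the seven-time list).

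**Precision: assumptions.** 42 patients, nine levels, equal variances over time, within-patient correlation ρ of 0.3 to 0.7, covariance treated as known. The target is the treatment difference averaged over time. Loss rates are assumed, because the documents give none per sample.

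*Loss only after the 24 h peak.* Let c be the share of patients with day-30 samples. The variance of one patient's nine-sample mean, in units of the single-sample variance, is (1 + 8ρ)/9. Split it into R, the part contributed by the day-30 samples that the early samples cannot predict, and A, the rest. The CI ratio, completers to all valid samples, is √[(A + R)/(cA + R)].

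At ρ = 0.5:
- A + R = 5/9 = 0.5556.
- The residual covariance of the two day-30 samples given seven early ones is 0.5 on the diagonal plus 0.5 − 7(0.25)/4 = 0.0625 throughout, so R = (2 × 0.5 + 4 × 0.0625)/81 = 0.0154 and A = 0.5401.
- c = 0.95: √(0.5556/0.5285) = 1.025.
- c = 34/42: √(0.5556/0.4527) = 1.108.
- c = 0.75: √(0.5556/0.4205) = 1.149.

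*Scattered losses.* Independent loss at rate p leaves 42(1 − p)⁹ complete patients. Clustered loss uses a beta-binomial with correlation 0.3. The all-valid-sample variance comes from generalized least squares over the missing-data patterns.

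| Assumed loss | Complete of 42 | CI wider by (ρ 0.3-0.7) |
|---|---|---|
| 5% of patients, after 24 h only | 39.9 | 2-3% |
| 19% (42 to 34), after 24 h only | 34 | 10-11% |
| 25%, all after 24 h (extreme) | 31.5 | 14-15% |
| Clustered, 1 / 3 / 5% per sample | 40.3 / 37.1 / 34.1 | 2 / 6 / 10-11% |
| Independent, 1 / 3% per sample | 38.4 / 31.9 | 5 / 14-15% |
| Independent, 5% per sample (extreme) | 26.5 | 25-26% |
| Same patients lose everything | 42(1 − p) | almost nothing |

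For the treatment contrast of day 30 minus the early average, loss confined to the period after 24 h costs only about 1% or less.

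**Does the remedy carry a risk?** Suppose samples correlate at 0.6-0.7 within the early block and within day 30, but at 0.2-0.4 between them. Of the 36 pairs, 21 + 1 are within a block and 14 between. A compound-symmetry fit estimates roughly the average: with 0.7 and 0.2, (22 × 0.7 + 14 × 0.2)/36 = 0.506. The interval for a 24 h-to-day-30 contrast is then √((1 − 0.506)/(1 − 0.2)) = 0.786 of its proper width. Over the assumed range it is about 11-21% too narrow, with large-sample coverage of about 88-92%. The choice of covariance can therefore cost as much as the recovered samples gain.

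**The case against.** The strongest reply is that nothing in the text prescribes deletion. The wording on between- and within-subject variation fits a mixed model, and a population of all patients with PD data, used for all primary and secondary PD variables, sits poorly with removing someone for one missing sample. This stands. A reader might infer that the plan mandates complete-case analysis; the documents show only that the procedure is open.

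A reader might also take the 25% allowance as the share lost between 24 h and day 30. It is not. It mixes drop-out, withdrawal, invalid samples and unplanned parenteral antiplatelet use, and some of those patients could leave the PD population under either method. The one related rate in the documents, 4.6% ticagrelor discontinuation for dyspnea (section *Possible Discomforts and Risk*), comes from longer trials. It would mean 0.046 × 21 = 0.97 patient, and a single-time-point interval under 1% wider: √[(55²/20 + 100²/21)/((55² + 100²)/21)] = 1.006. Even that assumes sampling stops, whereas the protocol says only that such patients are switched to clopidogrel.

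Finally, early treatment effects are already estimated from all valid samples in the single-time-point comparisons. This also stands, and it limits the priority. It does not remove the case for a method that uses the same data more fully at no cost in samples or software.

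**Conclusion.** The point holds as a low-priority improvement to a supportive secondary analysis, worth considering. If the across-time analysis is run in GLM Repeated Measures, each patient lost before day 30 forfeits up to seven valid samples (five under the secondary-endpoint list). Under moderate assumed losses the interval for the time-averaged difference is then about 2-11% wider than necessary. The 14-15% and 25-26% figures are outer extremes, and the cost is near zero if losses are rare or fall on the same patients. All these sizes depend on assumed loss rates, nine levels and a known compound-symmetry covariance, so the gain from a model estimated in about 42 patients may be somewhat smaller.

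The documents do not support reading this as a threat to the trial's main result: the primary day-30 trough ANOVA uses one sample per patient and loses nothing by this route.

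**What to change.** For the across-time analysis only, replace repeated-measures ANOVA with a linear mixed model:

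- SPSS MIXED, REML, Satterthwaite degrees of freedom, with treatment, categorical time and treatment-by-time.
- All valid samples from every PD-population patient with at least one post-LD sample.
- A list of the time levels, reconciling the nine samples in *Study design* with the seven in the secondary-endpoint list, which omits 2 h. Say whether end of PCI, which has no fixed clock time, is a level. Say also whether the pre-LD value is a level or a covariate and, if a covariate, what is done when it is missing.
- A prespecified covariance structure that does not force one correlation on early and day-30 samples and lets variances differ by arm (planning SDs 55 and 100). One example is a patient effect, a patient-by-period effect (up to 24 h; day 30) and a residual, each with its own variance by arm: 3 × 2 = 6 parameters, against 9 × 10/2 = 45 for an unstructured matrix. It assumes constant variance over time within an arm.
- A fallback if the model does not converge, for example the same structure common to both arms (3 parameters).
- A table of valid samples by arm and time point, with reasons for loss.

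The cost is SAP wording: same software, no extra patients or samples. The downsides are that the covariance must be fixed in advance and can be wrong in about 42 patients, and that the model relies on data missing at random, so it does not cure informative drop-out such as stopping for side effects.
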